#### 5 REGISTRATION

It is the responsibility of the Principal Investigator (PI), or a person delegated by the PI (as documented on the delegation log) to obtain written informed consent from each subject **prior** to participation in this study, following adequate explanation of the aims, methods, study procedures and any risks. Please refer to Appendix 6 for contingency measures during extenuating circumstances.

After each patient has given written informed consent and completed the necessary study specific procedures as set out under baseline procedures (section 6.1) and in the visit schedule (section 6.6), an eligibility checklist must be completed prior to registration. The following information will be required:

- Confirmation that the patient is eligible for the trial by completion of the checklist;
- Confirmation that the measurable disease being followed in the trial has been assessed by photography and/or MRI/ CT scan within 6 weeks of scheduled start date of treatment;
- Confirmation that the patient has given written informed consent;

Central registration will be performed by the investigator-led study (ILS) team part of the Clinical Trials Unit (Bristol Haematology and Oncology Centre), on behalf of the sponsor (UHBW). The checklist will be sent to the ILS team who will confirm eligibility and register the patient onto the trial. The patient will be assigned a unique trial identification number (Trial ID). This Trial ID is recorded on all documentation and will be used for identification purposes in the IMPACT study only.

To register a patient, please send the eligibility checklist by email to:

[contact] (08.30 – 17.00 Monday to Friday)

Patients should commence trial treatment within 3 weeks of registration.

#### 6 STUDY PROCEDURES AND EVALUATIONS

#### 6.1 **Baseline** (within 7 days of registration)

Patients will undergo general assessment and assessment of their disease to include:

- Physical examination to assess fitness (including height and weight); ECOG performance status; vital signs (blood pressure, heart rate, oxygen saturation, temperature).
- Recording of concomitant medication use, with relevant dates.
- Medial and cancer history.
- ECG.
- Photography of skin lesion(s), including those to be followed as target lesions within 6 weeks of scheduled start date of immunotherapy. Target lesions need to be ≥10mm in both the longest diameter and the perpendicular diameter.
- MRI/ CT scan (with IV contrast) of the area encompassing the primary tumour (e.g. head and neck, chest, abdomen etc) to be performed within 6 weeks of scheduled start date of immunotherapy. If the lesions are in the head and neck region an MRI scan would be preferred. This scan will document any deeper extent of disease and whether this modality will be used to follow any target lesion(s). The same modality used to document target lesion extent at baseline must be used throughout the study.
- Full blood count, U+Es (including urea, sodium, potassium, total calcium and creatinine), liver function tests (to include ALP, ALT, Albumin and Bilirubin), LDH, thyroid function tests (including TSH, T4 and if required T3), cortisol and glucose (random). NB cortisol levels need to be measured ideally before 9am.
- Viral screen to include HIV, Hepatitis B and Hepatitis C. Patients with well controlled HIV will need to show undetectable viral load and CD4 counts over 350 to confirm inclusion into the study.
- Serum pregnancy test if required
- Estimated GFR to be assessed according to local practice (recommended technique of eGFR using the CKD-EPI formula (see Appendix 3)).
- Baseline assessment of symptoms using common toxicity scoring (CTCAE v5.0).
- Completion of Quality of life questionnaires EQ-5D-5L, EORTC QLQ-C30, Skindex-16, FNAE and the Hornheide questionnaire.

# 6.2 **On-treatment** assessments (within 7 days prior to cycle 1 and then within 5 days prior to each subsequent cycle of treatment)

Patients will be seen and assessed prior to each cycle of treatment. Please refer to Appendix 6 for contingency measures during extenuating circumstances. Assessment should include:

- Limited symptom-directed physical examination including vital signs (weight, blood pressure, heart rate, oxygen saturation and temperature).
- ECOG performance status.
- Full blood count, U+Es (including urea, sodium, potassium, total calcium and creatinine), liver function tests (to include ALP, ALT, Albumin and Bilirubin) and LDH. Thyroid function tests (including TSH, T4 and if required T3), cortisol and glucose (random) to be performed at each pre-assessment up to and including cycle 5 then every other cycle.
- Serum pregnancy test if required

- Estimated GFR to be assessed according to local practice (preferred technique of eGFR using the CKD-EPI formula (see Appendix 3)).
- Toxicity assessment (CTCAE v5.0) from day 1 of treatment up to and including 95 days after the last trial treatment.
- Updated recording of concomitant medication use, with relevant dates.
- Photography of skin lesion(s), including those being followed as target lesions. To be performed 12 weeks (+/- 7 days) after cycle 1 day 1 and before cycle 5. Subsequent photography will be taken every 12 weeks (+/- 7 days) from the previous photography whilst patient is on treatment. NB Target lesions need to be measured in both the longest diameter and the perpendicular diameter.
- MRI/CT scan (with contrast) only if being used to follow target lesions. Use the same modality and scan the same areas as in the baseline scan. Scan 1 to be performed 12 weeks (+/- 7 days) after cycle 1 day 1 and before cycle 5. Subsequent scans will then be performed every 12 weeks (+/- 7 days) from the previous scan whilst patient is on treatment.
- Completion of Quality of life questionnaires EQ-5D-5L, EORTC QLQ-C30, Skindex-16, FNAE and the Hornheide questionnaire at pre cycle 5, 9, 13, 17, 21, 25, 29, 33, and end of treatment visits.

#### 6.3 End of treatment visit

Patients should be seen 3-6 weeks from the first day of their final cycle of treatment. Assessments should include:

- Limited symptom-directed physical examination including vital signs (weight, blood pressure, heart rate, oxygen saturation and temperature).
- ECOG performance status.
- Full blood count, U+Es (including urea, sodium, potassium, total calcium and creatinine), liver function tests (to include ALP, ALT, Albumin and Bilirubin) and LDH, thyroid function tests (including TSH, T4 and if required T3), cortisol and glucose (random).
- Serum pregnancy test if required
- Estimated GFR to be assessed according to local practice (preferred technique of eGFR using the CKD-EPI formula (see Appendix 3)).
- Toxicity assessment (CTCAE v5.0) from day 1 of treatment up to and including 95 days after the last trial treatment. Any AEs ongoing after this time will be followed to resolution.
- Updated recording of concomitant medication use, with relevant dates.
- Completion of Quality of life questionnaire EQ-5D-5L, EORTC QLQ-C30, Skindex-16, FNAE and the Hornheide questionnaire.

If the patient remains progression-free then the photography and MRI/CT scans will continue 12 weeks (+/- 7 days) from the previous scan

- Photography of skin lesion(s), including those being followed as target lesions.
   NB Target lesions need to be measured in both the longest diameter and the perpendicular diameter
- MRI/CT scan ONLY if being used to follow target lesions. Use the same modality and scan the same areas as in the baseline scan.

#### 6.4 **Follow-up** (3, 6, 9 and 12 months plus survival data at 18 and 24 months)

Patients will be seen and clinically assessed every 3 months from the first day of their final cycle of treatment for a total of 12 months. Please refer to Appendix 6 for

contingency measures during extenuating circumstances

#### 3 month safety visit

Patients should be seen 95 days (+/- 7 days) after the first day of their final cycle of treatment. Assessments should include:

- Limited symptom-directed physical examination including vital signs (weight, blood pressure, heart rate, oxygen saturation and temperature).
- ECOG performance status.
- Full blood count, U+Es (including urea, sodium, potassium, total calcium and creatinine), liver function tests (to include ALP, ALT, Albumin and Bilirubin) and LDH, thyroid function tests (including TSH, T4 and if required T3), cortisol and glucose (random).
- Serum pregnancy test if required
- Estimated GFR to be assessed according to local practice (preferred technique of eGFR using the CKD-EPI formula (see Appendix 2)).
- Toxicity assessment (CTCAE v5.0) from day 1 of treatment up to and including 95 days after the last trial treatment. Any AEs ongoing after this time will be followed to resolution.
- Updated recording of concomitant medication use, with relevant dates.

#### 6, 9 and 12 month follow up visits

Patients will be seen and clinically assessed every 3 months. Assessments should include:

- Limited physical examination including vital signs (weight, blood pressure, heart rate, oxygen saturation and temperature).
- ECOG performance status.

If the patient remains progression-free then the photography and MRI/CT scans will continue during the follow up period 12 weeks (+/- 7 days) from the previous scan until the 12 month follow up visit.

- Photography of skin lesion(s), including those being followed as target lesions.
   NB Target lesions need to be measured in both the longest diameter and the perpendicular diameter
- MRI/CT scan ONLY if being used to follow target lesions. Use the same modality and scan the same areas as in the baseline scan.

#### 18 and 24 month survival follow up

Survival data will be collected for all patients at 18 and 24 months post treatment.

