# 2.3 Secondary endpoints

- To evaluate safety and tolerability including the frequency, severity and relatedness of AEs to the study treatment. AEs will be assessed according to CTCAE v5.0.
- To assess ORR at 12 months and 24 months.
- To assess disease control rate (DCR) at 6, 12 and 24 months. DCR is ORR plus stable disease (SD).
- To assess progression-free survival (PFS) defined as the time from registration to the first of one of the following: development of clinical/radiological disease progression (composite criteria/ RECIST 1.1) or death from any cause.
- To assess overall survival (OS) defined as time from registration to the date of death from any cause.
- To assess patient health status and quality of life (QoL) using the patient reported outcome measures EQ-5D-5L, EORTC QLQ-C30, Skindex-16, FNAE and the Hornheide questionnaire.
- To estimate the time to response (TTR: defined as the time from the start of treatment to the first objective tumour response (tumour shrinkage of ≥30%)) and duration of response (DOR: the time from response to progression/death) to cemiplimab.

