#### 3 TRIAL DESIGN

This is a non-randomised, open, single arm, two-stage, multi-centre phase II trial evaluating efficacy of cemiplimab (continue until progression) in patients with IaBCC.

The trial aims to recruit 41 patients with laBCC, who will receive the following regimen:

cemiplimab 350mg on day 1 only of each 21 day cycle, over a maximum period of 2 years.

Assessment of response will be done after cycle 4 and then every 12 weeks whilst on trial and progression free.

The planned recruitment duration for this study is 2 years. Patients will have up to 24 months of treatment and will be followed for a further 24 months after treatment ends at 3, 6, 9, 12, 18 and 24 months.

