# 10 END OF STUDY (EOS)

Recruitment is planned for 24 months. Patients will be treated for up to 24 months and then followed up every 3 months for a further 12 months. Survival follow up will then be conducted at 18 and 24 months post end of treatment. The end of study is defined as last patient last visit (LPLV) which will be the last survival follow up visit (at 24 months after end of treatment) completed by a patient on the trial.

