#### Overall survival

 An overall survival curve will be generated using the methods of Kaplan and Meier. The median overall survival will be reported with 80% and 95% CI.

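### Survival follow-up is timed from each patient's end of treatment while overall survival is timed from registration, so the Kaplan-Meier curve beyond about month 25 can be biased

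*Protocol*

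**What the plan says.** **Time origin.** Section 2.3 lists the endpoint as "To assess overall survival (OS) defined as time from registration to the date of death from any cause".

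**End of survival collection.** Section 3 has patients "followed for a further 24 months after treatment ends at 3, 6, 9, 12, 18 and 24 months". The last part of section 6.4 states "Survival data will be collected for all patients at 18 and 24 months post treatment", and the last column of the visit schedule in section 6.6 is month 24 after treatment. Section 10 repeats it: "Survival follow up will then be conducted at 18 and 24 months post end of treatment". The same section closes the study at the last such contact, "which will be the last survival follow up visit (at 24 months after end of treatment) completed by a patient on the trial".

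**When treatment ends.** Sections 7.1 and 9.1 stop cemiplimab at progression, unacceptable toxicity, patient request (choosing curative surgery is named as an example) or non-compliance, with a ceiling of 24 months.

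**Analysis.** Section 11.4: "An overall survival curve will be generated using the methods of Kaplan and Meier". The median is to be reported with 80% and 95% confidence intervals.

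No section gives a common cut-off date for survival, or any collection of survival status later than 24 months after a patient's own end of treatment.

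**The concern.** The Kaplan-Meier method assumes that a patient censored at a given time has the same future risk as those still followed. Here the length of follow-up is set by the length of treatment, and treatment length reflects the patient's course. Those who stop early leave observation from about month 25. From then on the curve is carried more and more by patients who stayed on treatment. If short treatment goes with a worse outlook, the late part of the curve looks better than the truth.

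At stake are the late part of the OS curve and the median if it falls there. The analysis plan cannot repair this afterwards, because survival status that was never collected cannot be recovered. The collection schedule is fixed in the protocol, so that is where a correction belongs.

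**Working it through.** The protocol states no numerical OS figure to reproduce. The check therefore covers the calendar, then the size of the possible bias, then the median.

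**1. Censoring times from registration** (1 month = 30.4375 days)

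Inputs: start of treatment 0 to 3 weeks after registration (section 5); 21-day cycles, at most 34 cycles or 24 months (Trial Summary, section 7.1); last contact 24 months later. The start of that clock varies: section 6.4 counts visits "every 3 months from the first day of their final cycle of treatment", while section 9 allows end of treatment to fall up to 6 weeks after that day.

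- Stop after cycle 1, counted from day 1 of that cycle: 24 to 24 + 21/30.4375 = 24.0 to 24.7 months.
- The same patient, counted from an end of treatment 6 weeks later: up to 24 + 63/30.4375 = 26.1 months.
- Full course, cycle 34 day 1: 33 × 21 / 30.4375 = 22.8 months; + 24 = 46.8; with a 3-week lag, 47.5.
- Full 24 months of treatment plus lag: 24 + 24 + 0.7 = 48.7 months.

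Censoring thus runs from about month 25 to about months 47 to 49, ordered by treatment duration.

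**2. Size of the bias under assumptions**

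The documents give neither mortality by treatment duration nor the share stopping early, so both are assumed. A share f stops uniformly over months 0 to 12 and the rest at cycle 34 day 1. Death hazards are constant within each group. Each patient is censored 24 months after stopping. Kaplan-Meier from 400,000 simulated patients is compared with true survival

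S(t) = f(1 − a)^(t/12) + (1 − f)(1 − b)^(t/12),

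where a and b are annual mortality in early stoppers and in the others.

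Example, f = 0.5, a = 20%, b = 5%:
- At 36 months: 0.5 × 0.8³ + 0.5 × 0.95³ = 0.256 + 0.429 = 0.685 (simulated truth 0.686). Kaplan-Meier 0.704, bias +1.8 points.
- At 42 months: 0.5 × 0.8^3.5 + 0.5 × 0.95^3.5 = 0.229 + 0.418 = 0.647 (simulated truth 0.648). Kaplan-Meier 0.686, bias +3.8 points.
- About 44% of patients remain at risk at 36 months, nearly all of them long-treated.

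Bias in percentage points:

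| f | a / b | 36 mo | 42 mo | 46 mo |
|---|---|---|---|---|
| 30% | 10% / 5% | +0.5 | +1.1 | +1.4 |
| 30% | 20% / 10% | +0.8 | +1.6 | +2.0 |
| 30% | 20% / 5% | +1.2 | +2.4 | +3.1 |
| 30% | 30% / 5% | +1.5 | +2.9 | +3.7 |
| 50% | 10% / 5% | +0.7 | +1.6 | +2.2 |
| 50% | 20% / 10% | +1.2 | +2.5 | +3.3 |
| 50% | 20% / 5% | +1.8 | +3.8 | +5.0 |
| 50% | 30% / 5% | +2.4 | +4.7 | +6.0 |
| 30% or 50% | 5% / 5% | 0 | 0 | 0 |
| 30% | 3% / 6% | −0.4 | −0.7 | −1.0 |
| 50% | 3% / 6% | −0.5 | −1.2 | −1.7 |

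The bias is zero at 24 months throughout and, in the eight scenarios with higher early-stopper mortality, +0.1 to +0.5 points at 30 months. Following everyone to a common 46.8 months brings it to 0.000 in every row.

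**3. Against sampling error.** With 41 patients, in the 50%, 20% / 5% scenario, the standard error of the Kaplan-Meier estimate is 7.3 points at 36 months and 7.5 at 42.

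**4. The median.** In the table's scenarios true survival at 46 months is still at least 53.9%. Harsher assumptions (constant annual hazards) give true survival at 48 months of f·exp(−4h₁) + (1 − f)·exp(−4h₂):

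- f = 40%, hazards 0.15 / 0.05: 0.4 × 0.549 + 0.6 × 0.819 = 71%
- f = 40%, 0.25 / 0.05: 0.4 × 0.368 + 0.6 × 0.819 = 64%
- f = 60%, 0.25 / 0.05: 0.6 × 0.368 + 0.4 × 0.819 = 55%
- f = 60%, 0.30 / 0.08: 0.6 × 0.301 + 0.4 × 0.726 = 47%

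Only the last has a true median inside the longest follow-up.

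**The case against.** A reader might infer that the OS curve is biased upward as a matter of fact. The documents do not support that. They give no mortality by treatment duration, and several routes to short treatment do not imply a poor outlook. Section 9.1 names patient request, including a change of mind in favour of curative surgery. Appendix 2 foresees inoperable lesions becoming operable and counts clear margins as a partial response. Sections 7.5.4 and 9.1 let some patients continue past progression. Metastatic disease and ECOG 2 or worse are excluded, and section 1 describes BCC in general as slow growing with a good prognosis when appropriately treated, so high mortality in early stoppers is not a given. All this stands: sign and size rest on assumptions, and the last rows of the table show zero and negative bias.

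It is also fair that the protocol names no 36- or 42-month landmark, that the median would usually not be reached with or without a change, that the bias is smaller than the sampling error, and that the stage decision in section 11.1 uses response and not survival.

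What does not fall is the structure. Progression and toxicity are the main stated reasons to stop, and section 4.3 admits patients whose co-morbidities rule out surgery, so frailty may plausibly drive both stopping and death. The reported confidence intervals reflect sampling error only and would not reveal this bias.

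**Conclusion.** The point holds as a minor one. Survival collection is tied to each patient's own end of treatment, OS is timed from registration, and censoring therefore depends on treatment duration. Beyond about month 25 the Kaplan-Meier curve can be biased, most plausibly upward if early stoppers die at a higher rate.

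Under the assumed 10-30% against 5-10% annual mortality and 30-50% early stoppers, the bias is +0.5 to +2.4 points at 36 months and +1.1 to +4.7 at 42, against a standard error of about 7.5 points. It vanishes with equal hazards and reverses if early stoppers do better. Estimates up to month 24 are unaffected, and the median only if it lies beyond about month 25. Neither a definite upward bias nor a distorted median can be concluded from the documents. The primary endpoint is not touched.

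**What to change.** In sections 6.4, 6.6 and 10, keep the existing contacts and add one vital-status sweep at last patient last visit. It should cover every patient who has not withdrawn from survival data collection (section 9.2 already distinguishes that kind of withdrawal), whatever the date treatment stopped. Use that date as the common OS cut-off. Censoring of the patients covered then depends on when a patient registered and no longer on how long treatment lasted, and more patients stay at risk in the late part of the curve.

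The cost is one extra status query per early stopper and a change to the protocol wording, with consent wording if needed (the consent pages are not available to check). Study duration does not change. With 24 months of recruitment, up to 24 of treatment and 24 of follow-up, the trial may stay open for 24 + 24 + 24 = 72 months. A patient registered at the outset who stops after one cycle would otherwise go unobserved for about 72 − 25 = 47 of them.

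A fixed 48 months from registration would also give a common follow-up time, but it is less attractive: if late registrants stop early, the present end of study could fall before their month 48 and the trial would have to be extended.

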# 6.5 Procedures for assessing efficacy

6.5.1 Photography of skin lesions and MRI/CT scan of the area encompassing the primary tumour

The primary endpoint ORR will be assessed for externally visible tumour(s) which are

being used as target lesions using **clinical response criteria** (Appendix 2 table 1) according to World Health Organisation (WHO) criteria. This requires photography that shows bi-dimensional measurements (≥10mm in longitudinal dimension and ≥10mm in the perpendicular dimension). If patients only have target lesions being assessed radiologically using MRI/CT scan (target lesion ≥10mm in the longest diameter) ORR will be assessed using **RECIST 1.1 criteria**. Patients who have target lesions measurable by both clinical response criteria and radiologically by RECIST 1.1 will have their outcome assessed using **composite response criteria** (Appendix 2 table 2).

Please see Appendix 1 and Appendix 2 for more information.

The MRI/CT scan and photography must be completed at baseline (within 6 weeks of the first dose of trial treatment) in order to identify the target lesions. Photographs and scans must be sent to the study team for central review within 5 days of assessment. Please refer to the imaging manual for more information.

Objective tumour response to treatment will be assessed after cycle 4 (12 weeks +/-7 days from cycle 1 day 1) and before cycle 5, and then every 12 weeks (+/- 7 days from the previous photography/scan) whilst the patient is on treatment. If the patient stops treatment for any reason other than disease progression target lesions will continue to be assessed every 12 weeks (+/- 7 days) until disease progression for a maximum of 12 months. Photographs and scans must be sent to the study team for central review within 5 days of assessment. Please refer to the imaging manual for more information.

Please refer to Appendix 6 for contingency measures during extenuating circumstances.

Complete response can only be confirmed with clinical biopsy otherwise response remains as partial response.

Baseline	Scan 1	Subsequent scans	End pf treatment and in				
		on treatment	follow up				
Within 6 weeks of Cycle1 Day1	12 weeks (+/- 7 days) from Cycle1 Day1 but before Cycle 5	Every 12 weeks (+/- 7 days) from previous photography/scan	If no progression, photography and MRI/CT scans should continue every 12 weeks (+/- 7 days) from previous				
			photography/scan				

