#### Secondary:

- To evaluate safety and tolerability including the frequency, severity and relatedness of adverse events (AEs) to the study treatment. AEs will be assessed according to CTCAE v5.0.
- To assess ORR: Proportion of patients having achieved partial (PR) or complete (CR) remission at 12 and 24 months.
- To assess disease control rate (DCR) at 6, 12 and 24 months. DCR is ORR plus stable disease (SD)
- To assess progression-free survival (PFS) defined as the time from registration to the first of one of the following: development of clinical/radiological disease progression (composite criteria/RECIST 1.1) or death from any cause.
- To assess overall survival (OS) defined as time from registration to the date of death from any cause.
- To assess patient health status and quality of life (QoL) using the patient reported outcome measures EQ-5D-5L, EORTC QLQ-C30, Skindex-16, FNAE and the Hornheide questionnaire.

Trial Design

Open label, single arm, two stage, phase II non-randomised multi-centre trial

Type and number of patients

41 patients with locally advanced BCC will be recruited

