#### Treatment

Up to 34 cycles of treatment with cemiplimab alone (maximum of 24 months of treatment)

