#### 11.2 Analysis methods

All analyses will proceed using standard analytical techniques including Kaplan-Meier survival curves. Analysis will include tabulation of baseline characteristics of recruited patients. Intention to treat analysis will be used. Baseline characteristics for those patients not completing trial treatment will be tabulated for comparison with treated patients, to ensure the ability to generalise results. Baseline characteristics will include (but are not limited to) demographic data, tumour stage and grade. Categorical data will be reported as a percentage. Numeric data will be reported as median, mean, range and SD.

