# 11.4 Secondary endpoints

- ORR and DCR at 12m and 24m reported with 80% and 95% CI
- Progression-free survival
  - Progression free survival will be calculated from the date of registration until clinically or radiologically documented disease progression or death from any cause, whichever comes earlier.
  - Patients free from a progression event will be censored on the date of last follow up.
  - A progression-free survival curve will be generated using the methods of Kaplan and Meier. All patients registered in the study will be included. Median PFS rate will be reported with 80% and 95% CI.
  - Duration of response as measured by Kaplan-Meier at each follow-up, or until progression, will be reported.

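### Imaging ends 12 months after treatment stops, so 24-month disease control (and response, if it means current response) rests on carried-forward status for early stoppers and leans upward

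*Protocol*

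**What the plan says.** **Endpoints.** The trial summary lists as secondary the "Proportion of patients having achieved partial (PR) or complete (CR) remission at 12 and 24 months". Section 2.3 adds: "To assess disease control rate (DCR) at 6, 12 and 24 months. DCR is ORR plus stable disease (SD"). Section 11.4 plans "ORR and DCR at 12m and 24m reported with 80% and 95% CI", and section 11.2 states "Intention to treat analysis will be used".

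**Treatment length.** The summary allows "Up to 34 cycles of treatment with cemiplimab alone (maximum of 24 months of treatment").

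**Imaging after stopping.** For patients who stop for a reason other than progression, the text of section 6.5.1 says "target lesions will continue to be assessed every 12 weeks (+/- 7 days) until disease progression for a maximum of 12 months". Section 6.4 agrees: visits run "every 3 months from the first day of their final cycle of treatment for a total of 12 months", and photography and scans continue "12 weeks (+/- 7 days) from the previous scan until the 12 month follow up visit". The visit schedule in section 6.6 marks no photography or MRI/CT at 18 or 24 months after treatment. Only survival and anti-cancer therapy are listed there. The small table that closes section 6.5.1 tells sites to keep imaging progression-free patients every 12 weeks and gives no limit.

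**Missing data.** Section 11.5 prescribes last observation carried forward for uncollected data once a response assessment has taken place and no event has occurred. Patient-reported outcomes are exempt; response is not.

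**The concern.** A response or disease-control rate at 24 months needs each patient's tumour status at about month 24. The imaging limit, however, is counted from the end of treatment and not from entry. Section 9.1 foresees stopping without progression for toxicity, at the patient's request or for non-compliance. Patients who do so early, and who are still progression-free when their 12 months of imaging run out, leave the imaging schedule before month 24 even with perfect attendance.

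These patients are a selected group whose relapse after the last scan would go unseen. Under section 11.5 they enter the 24-month rates as still controlled or still responding. The binomial confidence intervals would treat that status as observed. Section 1 offers the potential for durable response as a reason for using anti-PD-1 therapy, so an upward lean in the 24-month figures matters to how the trial will be read.

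**Working it through.** **Inputs.** 34 cycles of 21 days (summary; section 3); imaging every 12 weeks from cycle 1 day 1 (section 6.5.1); limit of 12 months, counted from day 1 of the final cycle (section 6.4); 41 patients (section 4.2). One month is taken as 52.1775/12 = 4.348 weeks. Months are counted from cycle 1 day 1, and scans are assumed to fall exactly on the 12-week grid.

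**The plan's own figure.** 34 × 21 = 714 days = 102 weeks = 23.5 months, which agrees with the stated maximum of 24 months. The last dose falls at week 99 (22.8 months), so full-course patients are imaged well past month 24.

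**Last scan by stopping time.** The limit is m + 12, where m is the month of the final cycle. Month 24 is week 104.4.

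| Final cycle (month) | Imaging limit (month) | Last grid scan | Age of that scan at month 24 |
|---|---|---|---|
| 3 | 15 | week 60 (13.8 months) | 10.2 months |
| 6 | 18 | week 72 (16.6 months) | 7.4 months |
| 9 | 21 | week 84 (19.3 months) | 4.7 months |
| 11 | 23 | week 96 (22.1 months) | 1.9 months |
| 13 | 25 | week 108 (24.8 months) | scan falls after month 24 |

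**Where the cut lies.** The protocol sets no window for the 24-month assessment.
- If week 108 is required: (108 − 52.18)/4.348 = month 12.8, or 12.6 with the 7-day allowance.
- If the limit only has to reach month 24: month 12.
- If week 96 is accepted: (96 − 52.18)/4.348 = month 10.1.

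The heading of the visit schedule could suggest a clock that starts at the end-of-treatment visit, up to 6 weeks after day 1 of the last cycle. That moves each cut earlier by at most 6/4.348 = 1.4 months (for example 12 to 10.6). It would not remove the gap.

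**Direction.** Carry-forward counts a patient last seen in CR, PR or SD as controlled at month 24. The true status is either the same or an unseen progression, so the error in DCR cannot be negative. For ORR read as current response, a lost response is still counted. Only a new response after imaging ended would pull the other way.

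**Size.** Let k be the number who stop early and are alive and progression-free when imaging ends before month 24, and q the share of them who have relapsed unseen by month 24. The inflation of DCR is k × q / 41. One patient is worth at most 1/41 = 2.4 points. The documents give neither k nor q. If 10%, 20% or 30% of 41 were affected (4.1, 8.2 or 12.3; taken as 4, 8 or 12), the ceiling at q = 1 is:
- 4/41 = 9.8 points
- 8/41 = 19.5 points
- 12/41 = 29.3 points

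**Other time points.** Since m + 12 is never below 12, the limit does not truncate the 6- or 12-month rates.

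**The case against.** **Section 11.5 settles the handling.** A reader might infer that the 24-month rates cannot be calculated, or are biased in an unknown direction. The documents do not support this. The carry-forward rule fits these patients and yields a definite number. What stands is that the number is imputed from an old status and leans upward.

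**Not every early stopper is affected.** A reader might count everyone who stops before month 12 without progression. But a patient who progresses during the following 12 months of imaging has a known status. Deaths are captured too, because survival is followed to 24 months after treatment. The sizes above are therefore upper limits for any given early-stopping rate.

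**ORR may be cumulative.** The summary and section 11.3 speak of patients having achieved remission. The benchmark rates in section 11.1 rise with follow-up (42.9% to 47.6%; 47.0% to 56.1%), which is compatible with best response to date. On that reading an early stopper who responded is already counted, and only a first response after imaging ended would be missed. Section 2.3 and section 11.4 say only at 24 months, so the meaning is open. This objection stands for ORR. It does not help DCR.

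**The table in section 6.5.1 has no limit.** A reader might infer that imaging continues indefinitely. The text of the same section, section 6.4 and the visit schedule all say otherwise.

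**It belongs in the statistical analysis plan.** The choice of estimator could. But the endpoint, the imaging limit and the carry-forward rule are all fixed in the protocol, and an analysis plan that dropped carry-forward would contradict section 11.5.

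**Conclusion.** The point holds in a limited form. Patients who stop before about month 12 (10 to 13 on the section 6.4 clock) and are alive and progression-free when imaging ends have no tumour assessment near month 24. The stated rule then gives a 24-month DCR that can only be too high, and a 24-month ORR that leans the same way if it means current response. The ceiling of about 10 to 29 points rests on an assumed 10% to 30% of 41 affected and on all of them having relapsed unseen. The real effect will be smaller to the extent that early stoppers progress under imaging, die, or stay controlled. Only secondary endpoints at one time point are touched. The change is worth making because it is cheap.

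**What to change.** 1. In sections 11.4 and 11.5, exempt the 24-month ORR and DCR from carry-forward. Changing 11.4 alone would leave the two sections in conflict.
2. Estimate 24-month disease control as the Kaplan-Meier probability of being alive and progression-free at month 24, censoring at the last tumour assessment. This is the 24-month point of the PFS curve already planned, and the text should say so. Section 11.4 now censors PFS at the date of last follow-up, which could be a later contact without a tumour assessment. Use the last tumour assessment there too, and state how a death after imaging has ended is counted.
3. State whether 24-month ORR is best response by month 24 or current response at month 24. If current, estimate it by Aalen-Johansen with the same censoring.
4. Report how many patients' scheduled imaging ended before month 24. Show the carry-forward proportions at most as a sensitivity analysis.
5. Reconcile the table in section 6.5.1, which has no limit, with the text above it, section 6.4 and the visit schedule.

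**Cost.** Wording only: the data are already collected, and no visits or scans are added. The downside is that the estimates assume that the end of scheduled imaging is non-informative, which may not hold for patients who stopped for toxicity. That is still weaker than carry-forward's assumption that status does not change.
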